Appendix 3. A Logit-Normal GLMM for Longitudinal Binary Data and Tipping Point Analysis

A Logit-Normal Model

Let Y_{ij} be the binary outcome for subject i ($i = 1, 2, \dots, N$) and visit j ($j = 1, 2, 3, 4$). We assume $Y_{ij} = 1$ for a response and $Y_{ij} = 0$ for a non-response. Then we model as

$$P(Y_{ij} = 1 | x_{ij}, u_i) = \frac{e^{\beta' x_{ij} + u_i}}{1 + e^{\beta' x_{ij} + u_i}} \equiv \pi_{ij}(\beta; u_i)$$

Here, β is a vector of unknown parameters corresponding to the vector of fixed effects x_{ij} and u_i is a subject-specific random effect which is assumed to be normally distributed with mean 0 and variance σ^2 . Note that conditional on u_i , Y_{ij} is independent of Y_{ik} , when $j \neq k$.

The full marginal likelihood of the data is then,

$$L(\beta, \sigma^2) = \prod_{i=1}^N \int_{-\infty}^{\infty} \prod_{j=1}^4 \pi_{ij}(\beta; u_i)^{Y_{ij}} (1 - \pi_{ij}(\beta; u_i))^{(1-Y_{ij})} \times N(u_i; 0, \sigma^2) du_i$$

There is no closed analytical form for this likelihood.

For the present study, the primary endpoint is evaluated at Visit 8 / Week 12 ($j = 4$). There are three treatment groups, so the model term $\beta' x_{ij}$ when written out looks like,

$$\beta_0 + \sum_{k=1}^3 \beta_{1k} \times 1_{(T_i=k)} + \beta_{2j} + \sum_{k=1}^3 \beta_{3jk} \times 1_{(T_i=k)}$$

Here, T_i represents treatment for subject i . The third term in the expression is the effect for visit j and the fourth term in the expression is the interaction effect between treatment and visit. With an overall intercept term, the model is over-parameterized as written and so to fit the model, some restrictions on β are required. The default option (this can be changed using programming syntax) in standard statistical software is to assume $\beta_{13} = 0, \beta_{24} = 0$, thereby interpreting β_{11}, β_{12} as the difference in treatment effect relative to $T = 3$ and $\beta_{21}, \beta_{22}, \beta_{23}$ as the difference in visit effect relative to $V = 4$. Consequently, $\beta_{3jk} = 0$ when $j = 4$ or $k = 3$. So, for example, for a subject taking PF-04965842 100 mg QD at Week 12, the expression would be $\beta_0 + \beta_{11}$. For a subject taking PF-04965842 200 mg QD at Week 12, the expression would be $\beta_0 + \beta_{12}$. For a subject on placebo at Week 12, the expression would be β_0 .

Tipping Point Analysis

A method to analyze the longitudinal data of a binary endpoint measured during the placebo-controlled period (eg, IGA and EASI-75 response rates at Weeks 2, 4, 8 and 12) under the MNAR assumption is called the tipping point analysis. This tipping point analysis includes

two popular scenarios as special cases: (1) the Jump-to-Reference (JTR) analysis in which the response rate for a missing subject assessment in the active treatment group takes on (ie, jumps to) the rate for the reference or control treatment group and (2) the MAR analysis in which the response rate for a missing subject assessment in each treatment group is based on the posterior predictive response rate for that treatment group alone.

The saturated logit-normal GLMM as described above will be used as the imputation model. Estimation of the model parameters will be performed under the Bayesian framework using Markov Chain Monte Carlo (MCMC) methods. We assign a non-informative prior for each component of β to be independent and identically distributed as $\sim N(0, 10000)$ and assign a weakly informative prior for σ^2 as an Inverse-Gamma distribution with shape=1 and scale=1. With this prior distribution, the 90th percentile for σ^2 is approximately 9.

Let $\beta^b, u_i^b, b = 1, 2, \dots, B$ be a sample from the posterior distribution. A single imputation $\widetilde{Y}_{i,j}^b$ of missing $Y_{i,j}$ is based on the posterior predictive distribution of the response probabilities estimated from the GLMM. For example, if subject i is randomized to PF-04965842 100 mg QD ($T_i = 1$), then at Week 12 ($V = 4$),

$$\text{logit}(\pi_{i,1,4}^b) = \text{logit} \left(P(\widetilde{Y}_{i,4}^b = 1 | T_i = 1, V = 4) \right) = \beta_0^b + \beta_{11}^b + u_i^b.$$

If subject i is randomized to PF-04965842 200 mg QD ($T_i = 2$), then at Week 12 ($V = 4$),

$$\text{logit}(\pi_{i,2,4}^b) = \text{logit} \left(P(\widetilde{Y}_{i,4}^b = 1 | T_i = 2, V = 4) \right) = \beta_0^b + \beta_{12}^b + u_i^b.$$

If subject i is randomized to placebo ($T_i = 3$), then at Week 12 ($V = 4$),

$$\text{logit}(\pi_{i,3,4}^b) = \text{logit} \left(P(\widetilde{Y}_{i,4}^b = 1 | T_i = 3, V = 4) \right) = \beta_0^b + u_i^b.$$

In the tipping analysis, we apply a series of fixed quantities $\delta = (\delta_1, \delta_2)'$ to account for MNAR. We define,

$$\begin{aligned} \pi_{i,3,4}^{*b} &= \pi_{i,3,4}^b, \\ \pi_{i,1,4}^{*b} &= \delta_1 \pi_{i,3,4}^b + (1 - \delta_1) \pi_{i,1,4}^b, \\ \pi_{i,2,4}^{*b} &= \delta_2 \pi_{i,3,4}^b + (1 - \delta_2) \pi_{i,2,4}^b \end{aligned}$$

We then sample the single imputed value $\widetilde{Y}_{i,j}^b$ from a Bernoulli distribution with probability of success $\pi_{i,T_i,4}^{*b}$. For the present analysis, the responses from the placebo arm are not shifted.

Analysis of an imputed data set will produce an estimate as well as standard error of the treatment difference using CMH and normal approximation in [Section 5.2.1](#). For a given value of MNAR parameter δ , this is repeated for B (typically, $B=500$) times to generate B complete imputed data sets and these B sets of estimates are combined using the Rubin's

Method (Rubin, 1987). This can then be repeated for different values of MNAR parameter δ to evaluate the impact of missing data. Note that $\delta = (0, 0)'$ corresponds to an MAR analysis and $\delta = (1, 1)'$ corresponds to an analysis commonly known as Jump-To-Reference (JTR). As a special case, we will consider $\delta_1 = \delta_2$ for our analyses.

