5.3.1. Binary Endpoints

For binary endpoints analyzed at each scheduled visit separately, visit windows (see [Appendix 2](#)) will be used to map all observed data into nominal visits. After mapping, for subjects who drop out for any reason or require a rescue medication, any missing data will be defined as “non-responsive” from that point on at all subsequent visits; for other subjects, any observations missing intermittently (including baseline values) will be considered missing completely at random (MCAR) and will remain missing in the analysis.

Additional analyses that are based on statistical considerations will utilize the longitudinal nature of the binary endpoint. A Generalized Linear Mixed Model (GLMM) will be fit to the observed data (i.e., without defining missing data due to dropout as “non-response”). The binary outcome will be modeled using a logistic-normal distribution. Fixed factors will include treatment (PF-04965842 200 mg QD and 100 mg QD and the placebo group), visit (Weeks 2, 4, 8 and 12) and treatment-by-visit interaction. Visit will be modeled as a categorical covariate. A subject-specific random intercept will be used to model the correlation within a subject over time (see [Appendix 3](#)). Missing observations for the active groups will be imputed multiply using a tipping point analysis to estimate the treatment effect under the assumption that the missing data mechanism is missing at random (MAR) or more generally, is missing not at random (MNAR). Using the estimated posterior predictive distribution of the GLMM model parameters obtained using Markov Chain Monte Carlo (MCMC) methods, estimates of the posterior predictive probability of response will be calculated for each treatment group. For subjects with missing data at a visit, the posterior predictive response probability in each PF-04965842 dose group will be re-defined as a weighted linear combination of the posterior predictive response probability from this group and the posterior predictive response probability from the placebo group, where the missing observations in placebo group are assumed to be missing at random (MAR) (see [Appendix 3](#)). These weights are fixed MNAR quantities for the active groups. A single imputation of the missing value will be sampled from a Bernoulli distribution with this corresponding shifted / re-defined probability of response for the PF-04965842 dose groups.

090177e1912f28b6\Approved\Approved On: 26-Jun-2019 09:22 (GMT)

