This imputation will be repeated multiple times with different MCMC samples to obtain multiple completed datasets. For each such completed dataset, the estimates of the proportions and CMH-weighted difference of proportions between each PF-04965842 dose group and placebo will be obtained along with the associated standard errors using the methods in [Section 5.2.1](#). Rubin’s rule (Rubin, 1987) will be used to combine the multiple estimates and standard errors across the imputed datasets and provide p-values.

The above analysis can be repeated for different combinations of MNAR quantities which will be applied to the probability of response to assess when the conclusion might change (i.e., tipping). Two important scenarios are included in the tipping point analysis framework. When the MNAR quantities are zero and the posterior predictive probabilities in the PF-04965842 dose groups are not shifted, results are obtained under an assumption of MAR for the missing data mechanism. Alternatively, at the other extreme, when the MNAR quantities are 1.0 for each PF-04965842 dose group, results are obtained under an assumption that the distribution of the missing responses after discontinuation of either dose of PF-04965842 is the same as that of the missing responses on the placebo arm. More detailed descriptions are provided in [Appendix 3](#).

Due to a technical error in the process of transmission and collection of electronic data with the device, the data on the pruritus NRS scale was not collected from several subjects at the scheduled visits of Week 2 (Day 15) and after. This was not restricted to a particular site or country and was not indicative of being related to the missing value of pruritus endpoint or any other endpoints. As such, the missing data mechanism may be reasonably assumed to be missing completely at random or missing at random.

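### Cheap improvement: the tipping-point analysis never shifts placebo dropouts, so it omits the one direction that could overturn a co-primary result near the planned effects

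*SAP*

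**What the plan says.** The primary analysis of each co-primary endpoint counts dropouts as non-responders in every arm (SAP 6.1.1 and 6.2.1). For other gaps, SAP 5.3.1 says "any observations missing intermittently (including baseline values) will be considered missing completely at random (MCAR) and will remain missing in the analysis".

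The supportive analysis multiply imputes all missing responses from a longitudinal logistic model. Its stated purpose in SAP 5.3.1 is "to assess when the conclusion might change (i.e., tipping". Each active arm's missing-response probability is a weighted mix of its own and the placebo probability, with weight δ on placebo. δ = 0 is MAR. SAP 5.3.1 describes JTR as lying "at the other extreme, when the MNAR quantities are 1.0 for each PF-04965842 dose group". Appendix 3 adds "As a special case, we will consider" δ1 = δ2, and on placebo: "For the present analysis, the responses from the placebo arm are not shifted".

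Appendix 1 lists only two kinds of analysis for both co-primaries: non-responder (FAS and PPAS) and these tipping-point runs. SAP 6.1.2 names EASI-75 under the IGA heading, but Appendix 1 shows the runs for IGA as well. The PPAS requires observed Week 12 IGA and EASI scores (SAP 4.2), so it puts no stress on missing Week 12 data.

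**The concern.** A tipping-point analysis should move the missing-data assumption until the conclusion changes, or show that no assumption changes it. Here one end of the path (MAR) favours the active arms relative to the other, and the other end (JTR) roughly repeats the primary estimate. When the primary result is clear, a path between those ends will rarely tip.

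A result near plan could be overturned if active dropouts did not respond while placebo dropouts responded more often than MAR predicts. That direction is absent. The report could therefore not say how often placebo dropouts would have to respond before significance is lost, or that no such number exists. What is at stake is the strength of the robustness statement, not the primary test.

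**Working it through.** **Inputs.** From the sample size text (SAP 2.2; Protocol 9.1): 150 per active arm, 75 placebo; IGA 26% vs 6%; EASI-75 45% vs 15%; 5% level. From SAP 5.1, the 100 mg dose may be tested at 2.5% (critical z 2.24). Dropout is not stated, so every rate below is an assumption, written active/placebo. Calculations are unstratified and omit the random intercept.

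**1. Planned power, for orientation.** For IGA, the pooled rate is (39 + 4.5)/225 = 0.1933, null SE 0.0558, alternative SE 0.0451. Power = Φ[(0.20 − 1.96 × 0.0558)/0.0451] = Φ(2.01) = 97.8%. For EASI-75, Φ[(0.30 − 1.96 × 0.0675)/0.0579] = Φ(2.90) = 99.8%. These agree with the plan's at least 95% and at least 99%, and 0.95 × 0.99 = 0.9405 gives its 94%.

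**2. JTR against the primary.** Let c be the placebo completer rate. JTR adds (active dropout × c) to the active rate and (placebo dropout × c) to the placebo rate. So JTR minus primary = (active − placebo dropout) × c.
- Equal dropout: 0.
- 10%/20%: IGA −0.10 × 0.075 = −0.75 point; EASI-75 −0.10 × 0.1875 = −1.9 points.
- 15%/25%: IGA −0.10 × 0.08 = −0.8 point; EASI-75 −0.10 × 0.20 = −2.0 points.

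This is approximate. The model's u_i "is a subject-specific random effect which is assumed to be normally distributed with mean 0 and variance" is kept in the imputation, and intermittent gaps that the primary leaves missing are imputed.

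**3. Does the planned range tip?** Set completers at the planned rates. The variance is W = Σ r(1−r)/n, plus Σ m·p(1−p)/n² for imputation, plus Σ (m/n)²·p(1−p)/(completers) for the estimated probabilities, treated as independent.

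IGA at 30% dropout, JTR: active rate 0.7 × 0.26 + 0.3 × 0.06 = 0.20; difference 0.14; variance 0.001819 + 0.000338 + 0.000193 = 0.002350; SE 0.0485; z = 2.89.

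| Dropout per arm | IGA z, MAR to JTR | EASI-75 z, MAR to JTR |
|---|---|---|
| 5% | 4.32 to 4.18 | 5.05 to 4.83 |
| 10% | 4.21 to 3.93 | 4.92 to 4.49 |
| 20% | 3.97 to 3.41 | 4.64 to 3.81 |
| 30% | 3.71 to 2.89 | 4.34 to 3.15 |

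All exceed 1.96 and 2.24. JTR would first lose 5% significance at about 48% (IGA) or 50% (EASI-75) dropout per arm.

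**4. A borderline effect does tip.** Take IGA 16% vs 6% (24/150 vs 4.5/75, dropouts as non-responders) at 15%/25%. The primary pooled z is 2.13. By the step 3 variance, z is 2.16 at MAR (difference 0.108, SE 0.0501) and 1.89 at JTR (difference 0.092, SE 0.0486).

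**5. The omitted direction.** Set active dropouts to 0 and placebo dropouts to probability q. Non-responder rates are held at plan, so the completer rate is the planned rate/(1 − dropout). Both probabilities are fixed in advance, so only W and the imputation term apply.

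IGA at 20%/30%, q = 0.27: placebo rate (4.5 + 22.5 × 0.27)/75 = 0.141; difference 0.119; variance 0.002898 + 0.000788 = 0.003686; SE 0.0607; z = 1.96.

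The q at which 5% significance is lost, against the active completer rate:

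| Dropout | IGA | EASI-75 |
|---|---|---|
| 5%/5% | none | none |
| 10%/10% | 0.91 vs 0.29 | none |
| 10%/20% | 0.42 vs 0.29 | 0.81 vs 0.50 |
| 15%/25% | 0.33 vs 0.31 | 0.63 vs 0.53 |
| 25%/25% | 0.33 vs 0.35 | 0.63 vs 0.60 |
| 20%/30% | 0.27 vs 0.325 | 0.52 vs 0.56 |

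The threshold depends only on placebo dropout; active dropout changes the comparator. The 10%/10% IGA cell rests on fractional counts (4.5 responders, 7.5 dropouts). With 4 responders and 7 dropouts the lowest z is 2.09, with all 7 responding, so nothing tips.

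As plain counts, without the imputation term, 5% significance is lost when about 7 placebo dropouts respond for IGA (p 0.071 pooled, 0.052 unpooled) and about 13 for EASI-75 (0.068, 0.061).

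**The case against.** The placebo choice is disclosed, and the analysis is labelled supportive. The SAP version history attributes its introduction, in place of a JTR analysis, to a revision prompted by blinded data review and FDA input. The primary analysis is already harsher on active dropouts than JTR. Not tipping at a planned z of 3.58 (IGA) or 4.45 (EASI-75), pooled, is what a robust result should show. All of this stands, and it is why this is an improvement and not an error.

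Four further readings are tempting, and the documents do not support them.
- A reader might infer that the planned analysis cannot tip at all. Step 4 shows that it can when the effect is borderline.
- A reader might infer that the co-primary conclusions are fragile. Nothing here shows that; at low dropout no tipping cell exists.
- A reader might infer the opposite reassurance: that tipping always needs placebo dropouts to respond more often than active completers. That holds at 10%/20% and 15%/25%, but fails at 20%/30% for both endpoints and at 25%/25% for IGA. Since neither document gives a dropout rate, it cannot be stated in advance.
- A reader might fault δ1 = δ2. It does not restrict the tests, because each dose is compared with placebo separately (SAP Section 6) and uses only its own δ.

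Appendix 3 does not expressly bar δ above 1. That would push the active arms further down and still leave placebo unmoved.

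**Conclusion.** The point holds as a modest improvement to a supportive analysis. The only tipping path planned for the co-primaries runs from MAR to JTR on the active arms, with placebo fixed at MAR. At the planned rates and assumed dropout of 5% to 30% per arm it does not reach loss of significance at 5% or 2.5%; smaller effects can tip inside it. The direction that could overturn a result near plan is missing. How extreme that direction must be runs from no tipping point at 5%/5% to a placebo missing-response probability of 0.27 (IGA) or 0.52 (EASI-75) at 20%/30%.

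These figures rest on assumed dropout, planned response rates and a simplified unstratified model, so they indicate scale only. Type I error, the primary estimates and the primary test are unaffected.

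**What to change.** Amend SAP 5.3.1 and Appendix 3 to add an independent placebo shift. For each dose versus placebo and each co-primary endpoint, run a two-way grid with stated steps:
- active missing-response probability from its MAR value down to 0;
- placebo missing-response probability from its MAR value up to 1.

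Keep MAR and JTR as separately labelled points. Use the planned Rubin combination of the Section 5.2.1 standard errors. Report the cells where significance is lost at the alpha applying to that dose (5% for 200 mg; 5% or 2.5% for 100 mg), or state that none exist. Judge plausibility against the completer rates observed in both arms, with no general reassurance written beforehand.

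The cost is some SAP wording and more runs of existing code. The robustness statement may come out less favourable. The primary test does not change.

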Appendix 4. Investigator’s Global Assessment (IGA)

The Investigator’s Global Assessment of atopic dermatitis is scored on a 5-point scale (0-4), reflecting a global consideration of the erythema, induration and scaling. The clinical evaluator of atopic dermatitis will perform an assessment of the overall severity of atopic dermatitis and assign an IGA score and category as described in the table below. The assessment will be a static evaluation without regard to the score at a previous visit.

IGA Score

Score	Category	Description*
0	Clear	Atopic dermatitis is cleared, except for any residual discoloration (post-inflammatory hyperpigmentation and/or hypopigmentation).
1	Almost Clear	Overall, the atopic dermatitis is not entirely cleared and remaining lesions are light pink (not including post inflammatory hyperpigmentation) and/or; have barely palpable hard thickened skin and/or papules and/or; have barely perceptible lichenification; excoriation and oozing/crusting are absent.
2	Mild	Overall, the atopic dermatitis consists of lesions that are light red; with slight, but definite hard thickened skin and/or papules; with slight, but definite linear or picked scratch marks or penetrating surface injury; with slight, but definite thickened skin, fine skin markings, and lichenoid scale; oozing/crusting is absent.
3	Moderate	Overall, the atopic dermatitis consists of lesions that are red; with easily palpable moderate hard thickened skin and/or papules; with moderate linear or picked scratch marks or penetrating surface injury; with moderate thickened skin, coarse skin markings, and coarse lichenoid scale; with slight oozing/crusting.
4	Severe	Overall, the atopic dermatitis consists of lesions that are deep, dark red; with severe hard thickened skin and/or papules; with severe linear or picked scratch marks or penetrating surface injury; with severe thickened skin with very coarse skin markings and lichenoid scale; with moderate to severe oozing/crusting.

* The IGA will exclude scalp, palms, and soles from the assessment/scoring.

090177e1912f28b6\Approved\Approved On: 26-Jun-2019 09:22 (GMT)

Appendix 5. Eczema Area and Severity Index (EASI)

The EASI quantifies the severity of a subject’s atopic dermatitis based on both severity of lesion clinical signs and the percent of BSA affected. EASI is a composite scoring by the atopic dermatitis clinical evaluator of the degree of erythema, induration/papulation, excoriation, and lichenification (each scored separately) for each of four body regions, with adjustment for the percent of BSA involved for each body region and for the proportion of the body region to the whole body.

Lesion Severity by Clinical Signs: The basic characteristics of atopic dermatitis lesions-erythema, induration/papulation, excoriation, and lichenification-provide a means for assessing the severity of lesions. Assessment of these four main clinical signs is performed separately for four body regions: head and neck, upper limbs, trunk (including axillae and groin) and lower limbs (including buttocks). Average erythema, induration/papulation, excoriation, and lichenification are scored for each body region according to a 4-point scale: 0=absent; 1=mild; 2=moderate; 3=severe. Morphologic descriptors for each clinical sign severity score are shown in the table below.

Clinical Sign Severity Scoring Criteria for the EASI

Score		Description*
Erythema (E)		
0	Absent	None; may have residual discoloration (post-inflammatory hyperpigmentation and/or hypopigmentation).
1	Mild	Light pink to light red
2	Moderate	Red
3	Severe	Deep, dark red
Induration/Papulation (I)		
0	Absent	None
1	Mild	Barely palpable to slight, but definite hard thickened skin and/or papules
2	Moderate	Easily palpable moderate hard thickened skin and/or papules
3	Severe	Severe hard thickened skin and/or papules
Excoriation (Ex)		
0	Absent	None
1	Mild	Slight, but definite linear or picked scratch marks or penetrating surface injury
2	Moderate	Moderate linear or picked scratch marks or penetrating surface injury
3	Severe	Severe linear or picked scratch marks or penetrating surface injury
Lichenification (L)		
0	Absent	None
1	Mild	Barely perceptible to slight, but definite thickened skin, fine skin markings, and lichenoid scale
2	Moderate	Moderate thickened skin, coarse skin markings, and coarse lichenoid scale
3	Severe	Severe thickened skin with very coarse skin markings and lichenoid scale

* The EASI will exclude scalp, palms, and soles from the assessment/scoring.

090177e1912f28b6\Approved\Approved On: 26-Jun-2019 09:22 (GMT)

%BSA with Atopic Dermatitis: The number of handprints of skin afflicted with atopic dermatitis in a body region can be used to determine the extent (%) to which a body region is involved with atopic dermatitis (see table below). When measuring, the handprint unit refers to the size of each individual subject's hand with fingers in a closed position.

Handprint Determination of %BSA

Body Region	Total Number of Handprints in Body Region*	Surface Area of Body Region Equivalent of One Handprint*
Head and Neck	10	10%
Upper Limbs	20	5%
Trunk (including axillae and groin/genitals)	30	3.33%
Lower Limbs (including buttocks)	40	2.5%

Handprint refers to the hand size of each individual subject.

* The number of handprints will be for the entire body region; these values will not be adjusted for exclusion of scalp, palms, and soles from the BSA assessment.

EASI Area Score Criteria

Percent BSA with Atopic Dermatitis in a Body Region	Area Score
0%	0
>0 - <10%	1
10 - <30%	2
30 - <50%	3
50 - <70%	4
70 - <90%	5
90 - 100%	6

Body Region Weighting: Each body region is weighted according to its approximate percentage of the whole body (see table below).

EASI Body Region Weighting

Body Region	Body Region Weighting
Head and Neck	0.1
Upper Limbs	0.2
Trunk (including axillae and groin/genitals)	0.3
Lower Limbs (including buttocks)	0.4

* No adjustment for body regions excluded for assessment

090177e1912f28b6\Approved\Approved On: 26-Jun-2019 09:22 (GMT)

In each body region, the sum of the Clinical Signs Severity Scores for erythema, induration/papulation, excoriation, and lichenification is multiplied by the Area Score and by the Body Region Weighting to provide a body region value, which is then summed across all four body regions resulting in an EASI score as described in Equation below.

$$\text{EASI} = 0.1A_h(E_h+I_h+Ex_h+L_h) + 0.2A_u(E_u+I_u+Ex_u+L_u) + 0.3A_t(E_t+I_t+Ex_t+L_t) + 0.4A_l(E_l+I_l+Ex_l+L_l)$$

A = Area Score; E = erythema; I = induration/papulation; Ex = excoriation; L = lichenification; h = head and neck; u = upper limbs; t = trunk; l = lower limbs

The EASI score can vary in increments of 0.1 and range from 0.0 to 72.0, with higher scores representing greater severity of atopic dermatitis.

